Hence, we will also look for any differences in pain, nausea and vomiting over the first 24 hrs after the surgery, along with chances of readmission or ER visits within the same period, post discharge. At 3 months, we will look for the incidence of persisting pain after surgery.

Hypothesis

In patients who undergo ambulatory surgical procedures causing at least moderate pain, hydromorphone (HM) increases the proportion of patients who would demonstrate 'satisfactory analgesia [$=<4/10$ NAS] with minimal or no postoperative nausea-vomiting (PONV) [$<2/5$ VDS] as compared to morphine (M), when both are administered intravenously, in equianalgesic doses, and are compared at 2 hours after surgery in PACU.

2. Specific Objectives

The primary objective of this study is to compare the proportion of patients with SAME (satisfactory analgesia and minimal emesis) after AS, when using M compared with HM, during the immediate postoperative hospital stay.

Secondary objectives include:

1. Total dose of analgesic used in PACU, in morphine equivalents,
2. Time to discharge or readiness to discharge from the DSU,
3. Proportion of pain, and its comparison after discharge, within 24 hours,
4. Proportion of nausea, and its comparison after discharge, within 24 hours,
5. Proportion of vomiting, and its comparison after discharge, within 24 hours,
6. Incidence of CPSP at 3 months after discharge

The tertiary objectives include:

1. Proportion of patients with severe itching,

Protocol Version Date: Version 5 / June 23, 2015

Most Effective Opioid Analgesia in Ambulatory Surgeries: a randomized control, investigator blinded, parallel group with superiority design study of Morphine versus Hydromorphone

[name], Principal Investigator SJHH

[name], Principal Investigator HHS

2. Proportion of patients with significant sedation,
3. Proportion of patients with significant respiratory depression,
4. Patient satisfaction score at the time of discharge,
5. Time to discharge or readiness to discharge from the PACU,
6. Use of ketorolac as a rescue medication,

METHODS

The study is designed as a multisite, 2 arm, parallel, superiority design with randomization of patients and blinding of patients, health care providers (physicians and nurses) and research personnel (research coordinator and data analyst). Patients will be stratified based on site and laparoscopic/open surgeries. Intention to treat approach will be used for design and analysis.

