Allocation and Randomization: Treatment allocation will be done using a random, computer generated table, with an allocation ratio of 1:1, using random permuted block sizes. Stratification based on each centre (3 sites). These syringes (4*10 mls)-in sealed packages, labelled with serial numbers and no identifiers for the medication, shall be deposited in a safe drug locker, within the fridge, at the respective PACU. The actual randomization, for each patient happens as they enter into the PACU after surgery. The PACU nurse allotted for that patient will obtain the next medication package in series to be used for that patient. To ensure that the respective patient and medication is matched for subsequent analysis, the nurse will attach the medication sequence number on the patient study records, with no identifiers of actual drug. The PACU nurse shall also note down the patient hospital ID on the medication syringe, once it is taken out, to ensure there is no mix up.

Blinding: The study allocation will be blinded to patients, treating nurses, physicians, research assistant and investigators. The allocation order will be available only to the person responsible for randomizing and the pharmacists involved in the study at each centre.

Application of Intervention:

The Operating Room Protocol: Patients included in the study need to be managed according the OR protocol provided in Appendix 2. In brief, the patient will only have a GA, with local infiltration provided at the end of the surgery. Long acting opioid medications (morphine and hydromorphone) are not administered in the OR. LA infiltration is done within a range of 20-30 mls (based on laparoscopic or open surgeries) using 0.25% bupivacaine with or without adrenaline.

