At the end of 2 hours or after satisfactory completion of primary endpoints, patients shall be transferred to DSU. At the DSU, in both groups, patients shall be given oral Oxycocet (combination of oxycodone and paracetamol) or Tylenol 3 (combination of codeine and paracetamol), as a PRN medication, if necessitated by the patient's pain. Nurses shall note down the occurrence of any pain and nausea necessitating treatment in the patient's CRF. Readiness to discharge home is noted down for each patient. The RA shall collect the CRFs from PACU and DSU and deposit safely in a locked filing cabinet.

Planned Outcomes: Our combined primary outcome will be proportion of patients with SAME, as compared between the 2 groups. Analgesia will be based on NAS 0-10 (appendix 3), and PONV will be based on VDS 0-5 (appendix 3). These observations will be made at the end of 2 hrs or before (corresponding to the time of discharge from PACU), by the PACU nurse, in the specified CRF. All the other outcomes to be recorded within the hospital, along with the time of their measurement and proposed analysis method are noted in table 1.

Sample Size Calculation: It was calculated based on the primary, binary outcome of proportion of patients with SAME, which will be compared using a chi-square test. According to literature,

Most Effective Opioid Analgesia in Ambulatory Surgeries: a randomized control, investigator blinded, parallel group with superiority design study of Morphine versus Hydromorphone
 [name], Principal Investigator SJHH
 [name], Principal Investigator HHS

approximately 30%-40% of patients are provided with inadequate analgesia after their AS,^(25, 26) with a similar number also known to suffer from PONV after AS.^(3, 24) Our chart reviews suggests that approximately 20% of patients suffer from inadequate analgesia with PONV using morphine. For a 2-sided test, with an alpha of 0.05 and a power of 90%, and with an estimated effect size of 10% (p1= 80% and p2= 90%), a sample size of 266 per group was calculated. However, for recruitment we shall have a target of 275 per group, for a total of 550 patients (rounding off). For the primary outcome analysis, we expect minimal loss through attrition as the study involves a follow up of few hours. The expected recruitment is approximately 20 cases per month at each of the 3 sites. We expect the trial to run for 10-12 months.

Table 1: Study Outcomes, and their Measurement and Analysis

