4	Global Impression of Change	Likert scale 1-7

Most Effective Opioid Analgesia in Ambulatory Surgeries: a randomized control, investigator blinded, parallel group with superiority design study of Morphine versus Hydromorphone
[name], Principal Investigator SJHH
[name], Principal Investigator HHS

5	Analgesic Use: Did you have to use any pain medications for more than 1 month, to help with pain, which started with or after Surgery?	Yes or No
---	---	-----------

Statistical Analysis: The study will be analyzed using an intention to treat approach. The individual outcomes along with their respective analyses method have been listed within the table 1. Broadly the dichotomous outcomes will be reported as proportions and analyzed using a chi-square test to detect a significant difference ($p<0.05$). Precision will be reported using 95% CI. Continuous outcomes will be analyzed using an unpaired 2-tailed student t test for significance ($p<0.05$). Means and standard deviations shall be reported along with 95% CI. We also plan to perform logistic multivariable regression analysis to account for the influence of baseline covariates, which are listed in appendix 1. A sensitivity analysis will be performed to compare the effects of laparoscopic surgeries vs open surgeries.

Trial Management: This trial will be conducted at 3 hospital sites affiliated with McMaster University, Hamilton: St Joseph's Hospital, McMaster University Hospital and Juravinski Hospital.

Data Management and Quality Control: All study data including CRFs of each patient, shall be securely stored at the central office. A summary table indicating study timeline from enrollment to final follow-up (<http://www.spirit-statement.org/title/>) shall be included for each patient.⁽²⁷⁾ CRF's will be collected as paper forms. They shall be periodically cross-checked for completeness and entered into a suitable electronic master file. All reports of incorrect randomizations, protocol violations or incomplete data shall be noted.

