APPENDIX 1: Study Patient Case Record Form with Details to be Recorded

DEMOGRAPHICS AND PATIENT INFORMATION TO BE OBTAINED FROM PATIENT RECORDS

Study Number: Site: SJH MUMC JH

1	Patient's Hospital ID Number		
2	Age		
3	Gender	M	F
4	Height		
5	Weight		
6	Allergy to NSAIDS	Y	N
7	Allergy to LAs	Y	N

INFORMATION TO BE GAINED FROM THE PATIENT MEETING

1	APFEL Score (for PONV prediction)		Collected on 4 items- separately
2	HADS Score (Hospital Anxiety Depression Scale)		Collected on 14 items- separately
3	PCS (Pain Catastrophizing Scale)		Collected on 13 items - separately
4	Presence of Preoperative Pain in the Surgical Area	Y	N
5	If YES: is it Mild/ Moderate/ Severe		
6	Presence of Chronic Pain (>4 months) in Other Parts of the Body	Y	N

Most Effective Opioid Analgesia in Ambulatory Surgeries: a randomized control, investigator blinded, parallel group with superiority design study of Morphine versus Hydromorphone
 [name], Principal Investigator SJHH
 [name], Principal Investigator HHS

7	If YES: is it Mild/ Moderate/ Severe		
---	--------------------------------------	--	--

SURGICAL DETAILS TO BE OBTAINED FROM THE SURGICAL RECORDS

1	Date of Surgery		
2	Diagnosis (Intraoperative)		
3	Actual Surgical Procedure		
4	Laparoscopic or Open	L O	
5	Surgeon		Initials
6	Start Time of Surgery		
7	End Time of Surgery		
8	Duration of Surgery		
9	Total Local Anesthetic Infiltration (mls)		

ANESTHESIA DETAILS TO BE OBTAINED FROM THE ANESTHETIC RECORD

1	Anesthesiologist		Initials
2	Dexamethasone 4mg or 8mg	Y N	
3	Midazolam	1 mg 2 mg	
4	Propofol (total dose used)		
5	Remifentanyl (total dose used)		
6	Fentanyl (total dose used)		
7	Sufentanil (total dose used)		

Most Effective Opioid Analgesia in Ambulatory Surgeries: a randomized control, investigator blinded, parallel group with superiority design study of Morphine versus Hydromorphone
 [name], Principal Investigator SJHH
 [name], Principal Investigator HHS

8	Any continuous infusion used	Propofol  Remifentanyl 	
9	Ondansetron Prophylaxis Dose		Given prior to extubation
10	Was there a delay in transferring patient to the PACU (applicable when the PACU is on hold-and protocol needs to be initiated by the OR anesthesiologist)	Y N	

APFEL SCORE: for Prediction of Post-Operative Nausea Vomiting

RISK FACTOR	SCORE (each gets 0 or 1)
Postoperative Opioids	
Non-smoker	
Female Gender	
History of PONV or Motion Sickness	
Total Score	

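### The Methods overview stratifies by site and surgical approach, the allocation section by site only, and the primary chi-square test uses neither

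*Combined protocol and SAP*

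**What the plan says.** The design paragraph that opens METHODS states: "Patients will be stratified based on site and laparoscopic/open surgeries". With three sites and two approaches, that makes six strata.

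Allocation and Randomization gives a different list: "Stratification based on each centre (3 sites", which makes three strata. It specifies 1:1 allocation in permuted blocks, with serially numbered packages stored at each PACU. On issue it says: "The PACU nurse allotted for that patient will obtain the next medication package in series to be used for that patient". It mentions no separate laparoscopic and open series. On timing it says: "The actual randomization, for each patient happens as they enter into the PACU after surgery".

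The primary test is unstratified wherever it is stated. Sample Size Calculation refers to the "proportion of patients with SAME, which will be compared using a chi-square test", Table 1 lists chi-square for the primary outcome, and Statistical Analysis says that "dichotomous outcomes will be reported as proportions and analyzed using a chi-square test to detect a significant difference".

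Statistical Analysis also plans a multivariable logistic regression on the Appendix 1 covariates, and states: "A sensitivity analysis will be performed to compare the effects of laparoscopic surgeries vs open surgeries". The Appendix 1 case record form has a site field and a field headed "Laparoscopic or Open". Neither is named as a required term in the regression.

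**The concern.** The allocation section is the one a pharmacist would work from. A site-stratified list can be built from it, but that list does not deliver the stratification the Methods overview promises. If it is used, a report repeating the Methods sentence will be wrong. If the Methods sentence is what was intended, each PACU needs two package series and the nurse needs a rule for choosing between them. Neither is described.

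The second issue is the match between design and analysis. Blocking on a prognostic factor removes that factor's variation from the difference between arms. A plain chi-square still counts it in the standard error, so the test becomes conservative. A prognostic factor that is recorded but not blocked is also worth using, because adjusting for it recovers some power.

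**Working it through.** **The plan's own figure.** Inputs from Sample Size Calculation: 80% versus 90%, two-sided alpha 0.05, power 90%. With pooled variance under the null and no continuity correction:

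n = [1.960 × √(2 × 0.85 × 0.15) + 1.282 × √(0.80 × 0.20 + 0.90 × 0.10)]² / 0.10² = (0.990 + 0.641)² / 0.01 ≈ 266 per group.

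This matches the stated 266. At the recruitment target of 275 per group, z = (0.10 × √275 − 0.990) / 0.5 = 1.337, which is 90.9% power.

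**Imbalance in approach.** The documents give no laparoscopic share, so 50% is assumed. If approach is not blocked, the 95% range of the between-arm difference is ±1.96 × √(2 × 0.5 × 0.5 / 275) = ±0.084, or 8.4 points. Simulation gave the same 8.4 points with site-only blocks and 0.8 points with both factors blocked. If SAME rates differed by 20 points between approaches (assumed), an 8.4-point imbalance would shift the arm difference by 0.084 × 20 = 1.7 points. This is chance variation, not bias.

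**Chi-square against CMH.** The documents give no SAME rates by site or approach, so these are assumed. Set-up: 550 patients, three equal sites, 50% laparoscopic, permuted blocks of 4 or 6 (block sizes are not stated), constant odds ratio, overall SAME 80% versus 90%, 20,000 trials per cell. CMH uses six strata. Monte Carlo standard error is about 0.15 points for alpha and 0.2 for power. Entries are chi-square / CMH, in percent.

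| Assumed control SAME rates | Site-only blocks: alpha | Site-only blocks: power | Six-stratum blocks: alpha | Six-stratum blocks: power |
|---|---|---|---|---|
| Approach matters, 70/90 | 5.0 / 5.1 | 91.6 / 92.5 | 4.4 / 5.1 | 92.1 / 92.9 |
| Site matters, 70/80/90 | 4.6 / 5.0 | 91.5 / 92.0 | 4.5 / 5.0 | 92.1 / 92.6 |
| Both matter, 61-95 | 4.7 / 5.1 | 91.9 / 93.0 | 4.3 / 4.9 | 92.1 / 93.0 |
| Both matter, 54-98 | 4.6 / 4.8 | 91.7 / 93.9 | 3.5 / 5.1 | 92.7 / 94.2 |
| No stratum effect | – | 91.5 / 91.3 | – | 91.2 / 91.1 |

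Where the strata are prognostic, CMH gains 0.5 to 2.2 points of power with site-only blocks and 0.5 to 1.5 points with six strata. Where they are not, it costs at most 0.2 points.

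**Different assumptions.** A second simulation took 60% laparoscopic and expressed stratum effects as log-odds shifts: −0.5/0/+0.5 by site and ±0.5 by approach (moderate), or twice those (strong). It used 10,000 null and 5,000 alternative trials per setting.

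- Moderate, six strata: alpha 4.5 / 5.0, power 91.8 / 92.4.
- Strong, six strata: alpha 3.0 / 5.2, power 93.9 / 95.8.
- Strong, site-only blocks: alpha 4.1 / 4.8, power 91.2 / 95.0, a gain of 3.8 points.

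**The case against.** The strongest reply is that only the wording is at fault. The allocation section is operative and workable alone, and the Methods sentence is a one-line overview. An unadjusted chi-square is a legitimate prespecified test, valid under either allocation, and it agrees with the sample size calculation. Adjustment is already planned through the logistic regression, whose source form records site and approach. If approach is dropped as a stratum, analysing by the randomisation factors supports site only, and adding approach becomes ordinary covariate adjustment.

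The sizes also depend on generous assumptions. Each prognostic scenario in the table spans at least 20 points of control SAME. With a smaller gap (approach only, 75% versus 85%, 3,000 trials), CMH gained only about 0.1-0.2 points and chi-square alpha was 4.6-4.8%, with a Monte Carlo standard error of about 0.4-0.5 points per rate. The 1.7-point shift uses an extreme imbalance. The mean absolute imbalance is about 3.4 points, which gives 0.034 × 20 = 0.7 points, and the chi-square standard error already allows for that.

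Most of this stands as a limit on size. It does not remove the contradiction, since the Methods sentence names site and approach together as stratification factors. The regression is not primary and names neither factor as a term. The case for including approach under site-only allocation is efficiency, and should be described that way.

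**Conclusion.** The concern holds. The current text gives two incompatible sets of stratification factors, and the primary test reflects neither. The contradiction is the main point, because it leaves open whether three or six lists are needed and whether each PACU holds one package series or two.

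The analytic part is modest. Type I error is not inflated, chance imbalance in approach is not bias, power stays above 90% at 275 per group, and the sample size does not change. The chi-square gives up between almost nothing and about 2 points of power, and nearly 4 in the strongest setting tried. With six blocked strata its true alpha may fall to between 3.0% and 4.5% when the strata are prognostic. All of these ranges rest on assumed stratum rates, laparoscopic shares, site sizes and block sizes. The point should be corrected, but it does not threaten the trial's validity.

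**What to change.** 1. State one set of factors in both places. Either remove surgical approach from the Methods sentence, or add to Allocation and Randomization that each PACU holds separate laparoscopic and open permuted-block series and that the nurse draws from the series for the approach performed. The second option is feasible because approach is known before randomisation at PACU entry. If lists already exist, the text should describe what was actually generated.

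2. Make the primary test a CMH test stratified by site and approach as performed, with a Mantel-Haenszel risk difference and 95% CI. Keep the plain chi-square as supportive. Change Sample Size Calculation, Table 1 and Statistical Analysis together. If the chi-square stays primary, at least name site and approach as required terms in the planned logistic regression.

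The cost is wording only if approach is dropped as a stratum, because both variables are already on the case record form. Keeping it means splitting the refrigerated packages into two series per site, with some risk of a package being drawn from the wrong one. The target stays at 275 per group, with no added data collection.

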PACU Stay: The actual study intervention (hence randomization) will only become applicable once the patient is moved to the PACU. Every patient will be treated as per the protocol during the intraoperative management, which primarily restricts the use of any study opioids. The details are provided in appendix 2. The nurse looking after the study patient in PACU will administer the medication as per the study protocol. This would include analgesia with equipotent doses of M or HM administered in titrated doses. Syringes will be pre-prepared from the pharmacy in EMUs; 1ml=1mg of morphine or 0.2 mg of hydromorphone. We shall consider a potency ratio of 1:5 (M: HM), considered equivalent in literature.⁽⁹⁾ Analgesia will be provided according to the following guideline. A similar method has been advised to be safe and effective for titrated analgesia in PACU.⁽²⁴⁾ Readiness to discharge from PACU and outcomes are noted at 2 hrs, or at the time of discharge to DSU.

Most Effective Opioid Analgesia in Ambulatory Surgeries: a randomized control, investigator blinded, parallel group with superiority design study of Morphine versus Hydromorphone
[name], Principal Investigator SJHH
[name], Principal Investigator HHS

PACU Protocol (titrate the opioid medication to achieve desired pain score)

- Patient to be asked for their pain score, and if it is more than 4 out of 10 (NAS): to receive the 1st dose within 5 minutes after coming to PACU: 0.04mg/kg morphine units (rounding off to the nearest 1 ml or 0.5 ml); with a maximum of 3 mg of morphine equivalents.
- Repeat doses: 0.02 mg/kg morphine units every 5-10 minutes to titrate for analgesia and side effects (rounding off to the nearest 1 ml or 0.5 ml)
- If no side effects observed-titrate to have analgesia: NAS =<4/10.
- If Nausea-Vomiting observed: record it in the CRF provided and treat it with antiemetics (Ondansetron 1-4 mg IV, Dimenhydrinate 25-50 mg)
- If patient is too sedated (<3-Ramsey Sedation Scale)-withhold the next dose and restart the bolus if the score is >3
- If respiratory depression present, withhold the next dose, treat with Naloxone if necessary.
- Ketorolac IV 15-30 mg as rescue medication if patient does not tolerate the study opioid or if the patient does not satisfy the success of satisfactory analgesia at more than 1 hr.

DSU Stay and Protocol:

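### Randomising at PACU entry but dosing only above NAS 4 keeps never-dosed patients in the primary analysis and can cost power; allocating at the first NAS above 4 avoids this at modest cost

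*Combined protocol and SAP*

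**What the plan says.** - **Allocation.** Allocation and Randomization: "The actual randomization, for each patient happens as they enter into the PACU after surgery". The PACU nurse then takes the next sealed, numbered package. The PACU Stay section gives the rationale: "The actual study intervention (hence randomization) will only become applicable once the patient is moved to the PACU".
- **Dosing gate.** PACU Protocol: "Patient to be asked for their pain score, and if it is more than 4 out of 10 (NAS): to receive the 1st dose". The first dose is due within 5 minutes of arrival.
- **Analysis.** Methods: "Intention to treat approach will be used for design and analysis". Statistical Analysis: "The study will be analyzed using an intention to treat approach".
- **Success (SAME).** Table 1 requires NAS of 4 or less and a PONV score (VDS) below 2, at 2 hours or at PACU discharge.
- **Target comparison.** The Hypothesis compares the drugs "when both are administered intravenously, in equianalgesic doses, and are compared at 2 hours after surgery in PACU".
- **Sample size.** 80% versus 90% with SAME, 266 per group, recruitment target 275. The morphine rate rests on a chart review in which "approximately 20% of patients suffer from inadequate analgesia with PONV using morphine".

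No section estimates how many randomised patients will never be dosed, allows for them in the sample size, or defines an analysis without them.

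**The concern.** A patient who stays at or below NAS 4 throughout the PACU stay is randomised, receives neither drug and remains in the primary comparison. The dosing gate and the analgesia criterion share one cut-off, so such a patient meets the analgesia half of SAME and will usually be a success unless nauseated. The allocated drug cannot affect that result. A share f of these patients leaves the two arms comparable but pulls them together.

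What is at stake is the chance of detecting a real difference between the drugs in patients who receive them. The sample size has little slack: 266 is raised only to 275, and the accompanying remark concerns attrition, not patients who need no opioid.

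**Working it through.** **Inputs from the documents.** Two-sided alpha 0.05; power 90%; p1 = 0.80, p2 = 0.90; chi-square test; 1:1 allocation; 275 per arm; 20 patients per month at each of 3 sites, so 60 per month.

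**Assumptions (not in the documents).** Never-dosed share f = 5%, 10%, 20% or 30%. Never-dosed SAME rate q = 80–100%, equal in both arms.

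**1. The plan's figure.** With d = 0.10 and mean rate p̄ = 0.85,

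n = [1.960 × √(2 × 0.85 × 0.15) + 1.282 × √(0.80 × 0.20 + 0.90 × 0.10)]² / 0.10² = (0.990 + 0.641)² / 0.01, which rounds up to 266 per arm.

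This matches the plan. Power is Φ{[d√n − 1.960 × √(2p̄(1 − p̄))] / √(p1(1 − p1) + p2(1 − p2))}: 90.0% at 266 and 90.9% at 275.

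**2. If 80/90 describes dosed patients.** Each arm's rate becomes (1 − f)p + fq, and the difference becomes (1 − f) × 10 points. Example with f = 20%, q = 90%: the rates are 0.82 and 0.90, and Φ[(0.08 × √275 − 1.960 × √(2 × 0.86 × 0.14)) / √(0.1476 + 0.09)] = Φ(0.749) = 77.3%. The comparison restricted to NAS above 4 keeps 80% versus 90% with n = 275(1 − f). At f = 20%, n = 220 and power is Φ[(0.10 × √220 − 0.990) / 0.5] = Φ(0.987) = 83.8%.

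| f | All randomised, 275 per arm (q = 80–100%) | NAS above 4, same 550 patients |
|---|---|---|
| 5% | 87.5–89.2% | 89.5% |
| 10% | 83.2–87.2% | 87.8% |
| 20% | 72.7–82.5% | 83.8% |
| 30% | 60.0–76.5% | 78.7% |

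The restricted comparison has the higher power in every row and at every q tried.

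**3. If 80/90 describes all randomised patients.** The planned 90.9% stands. The implied dosed-patient rates are (0.80 − fq)/(1 − f) and (0.90 − fq)/(1 − f). With n = 275(1 − f) and q = 90–95%, the NAS-above-4 comparison has power of 91.6–91.9%, 92.2–92.9%, 93.5–94.7% and 94.7–96.3% at the four values of f. It is also higher than 90.9% across q = 80–100%.

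**4. Moving allocation, like for like.** With 275 dosed patients per arm at 80/90, power is 90.9% whatever f is, but this takes 550/(1 − f) consents: 579, 612, 688 or 786. The fair comparator is the present design with that many patients, n = 275/(1 − f) per arm. For q = 90–95% that design gives 88.7–89.6% at f = 10% and 85.8–87.8% at f = 20%. The gain from moving allocation is then 90.9 minus those figures: about 1–2 points and 3–5 points. Over q = 80–100% the gain is 0.5–4.0 and 1.0–9.2 points.

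**The case against.** The strongest reply is that analysing everyone randomised at PACU entry is a legitimate choice. The Risk Assessment section calls the trial pragmatic, and Methods commits to intention to treat for design as well as analysis. That stands: the comparison is valid as written.

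Second, f may be small. Eligibility is limited to surgery expected to cause at least moderate pain, and long-acting opioids and NSAIDs are barred in theatre. Local infiltration works the other way, and eligibility goes by type of operation, not by observed pain. The documents do not settle f. At 5% the loss is small.

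Third, 80/90 may already cover all randomised patients. The chart-review wording and the Hypothesis point to treated patients, while the commitment to intention to treat for design points the other way. If 80/90 is the all-comer rate, there is no shortfall against plan.

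Fourth, the PACU Stay sentence need not conflict with the dosing gate. The study intervention can mean the whole ask, score and titrate procedure, which begins for everyone on arrival. That is a fair reading, and the point does not depend on a contradiction there.

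What remains is that, under both readings of 80/90, the comparison among patients above NAS 4 is the more sensitive one. It also answers the question that the Hypothesis asks.

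**Conclusion.** The point holds as an inexpensive improvement to the design, not as an error that invalidates it. The direction is firm: within the ranges tried, never-dosed patients always reduce sensitivity. The size is conditional on f, on q and on which patients 80/90 describes. If it describes dosed patients, the loss is small at f = 5% and becomes material from about 10%.

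Three stronger readings are tempting, and the documents do not support them:

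- **That the analysis is biased.** Whether a patient first exceeds NAS 4 is determined before any study drug and under blinding, so never-dosed patients should fall evenly across arms.
- **That the trial is underpowered.** This would need a known f and the dosed-patient reading of 80/90. Neither is given.
- **That moving allocation restores about 91% at no cost.** That figure also uses more consented patients. With equal numbers consented, the gain is about 1–2 points at f = 10% and 3–5 points at f = 20% (q = 90–95%).

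**What to change.** **Preferred.** Draw the next numbered package when the first NAS above 4 is recorded, before any study drug. Everyone randomised is then due study drug, and intention to treat is kept in full. No dosing rule changes.

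**Alternative.** Leave allocation as it is and prespecify an analysis of all randomised patients with NAS above 4 recorded before any study drug, reported with the all-randomised analysis.

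**Either way.** State whether 80/90 refers to dosed or to all randomised patients, and report never-dosed numbers (by arm if allocation is unchanged). The PACU record form is not reproduced in the protocol, so confirm that it captures the score before the first dose.

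**Costs.**
- Keeping 550 allocated needs 579, 612, 688 or 786 consents at f = 5%, 10%, 20% or 30%. At 60 per month that is 9.6, 10.2, 11.5 or 13.1 months. The plan's own forecast is slower ("We expect the trial to run for 10-12 months"); dividing it by (1 − f) gives 10.5–12.6 months at f = 5% and 14.3–17.1 at f = 30%.
- The alternative needs no extra patients, but analyses only 275(1 − f) per arm: about 261, 248, 220 or 193.
- The population narrows to patients who need opioid in the PACU. Study Significance promises estimates of post-discharge symptoms and persistent pain. If these are to cover all day-surgery patients, consented but unallocated patients should stay in the 24-hour and 3-month follow-up.
- Drawing and labelling the package after the score must fit the 5-minute window in the PACU Protocol.

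**Separately.** Appendix 1 foresees the OR anesthesiologist starting the protocol when the PACU is on hold. This must be reconciled with allocation at PACU entry, so that the moment of randomisation has one definition.
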